6.4 Risks and Benefits

6.4.1 Potential Risks associated with KD025

KD025 has generally been well tolerated across the clinical studies conducted. No drug-related AEs have resulted in fatal outcomes. The most common AEs associated with KD025 administration are liver-related, specifically increased ALT and AST levels, but no Hy's Law cases. Subjects will receive single doses of KD025 in this study and will be closely monitored throughout the study for any changes in liver enzymes, and no subject with a history or presence of hepatic disease or ALT/AST values > the upper limit of normal (ULN) will be enrolled in the study (see Section 9.3).

Other commonly reported events include rash, pruritus, upper respiratory infection, joint aches and swelling, headache, fatigue, back pain, leg weakness, diarrhoea, nausea, vomiting, upper abdominal pain, increase in white blood cell count, cannula site infection, dizziness, and flatulence.

6.4.2 Risks associated with Radiation Exposure

The [¹⁴C]-KD025 solution for infusion and [¹⁴C]-KD025 capsule will contain a radionuclide (NMT 9.8 MBq [267 µCi]) so subjects will be exposed to ionising radiation. The effective dose that each subject will receive from one administration will not exceed 3 mSv. This is approximately 1 year and 1 month of the average radiation exposure received in the UK each year (2.7 mSv). It is believed that any increase in the amount of radiation that is received above natural radiation carries a risk of later developing serious and possibly fatal conditions. The risk associated with the maximum possible dose of radiation in this study is very small indeed and is considered to be acceptable.

6.4.3 Risks associated with exposure to Radiation Microdose

The IV micro dose to be administered is 2000-fold lower than the oral dose and the exposure to [¹⁴C]-KD025 originating from the infused micro dose is therefore considered negligible and no AEs are expected to occur.

6.4.4 Other considerations

During cannulation, more than one attempt may be needed to insert the cannula in a vein of a subject and it is possible that bruising and/or inflammation may be experienced at the site of cannulation.

Electrocardiogram stickers on the subjects' chests and limbs may cause some local irritation and may be uncomfortable to remove but subjects will be closely monitored to ensure any local irritation does not persist.

Although KD025 nonclinical data suggests the potential for phototoxicity, in standard reporting of AEs in Phase 1/2 clinical studies, KD025 has not demonstrated any clinically significant phototoxicity. Therefore, for this study no restrictions have been applied.

The blood volume taken for each subject will be approximately 583.5 mL in a 4 week period. To account for this, subjects with blood platelet count, haemoglobin and red blood cells lower than the reference range will be excluded from the study.

There is no benefit to the subjects from taking part in this study. The development of a ROCK2-selective small molecule drug has the potential for effectiveness in multiple disease indications and will be of benefit to the wider community.

The overall risk benefit balance is therefore considered to be acceptable.

7 Objectives and Endpoints

7.1 Objectives

7.1.1 Primary Objectives

- To determine the absolute oral bioavailability of KD025 (Part 1)
- To determine the mass balance recovery after a single oral dose of [¹⁴C]-KD025 (Part 2)
- To provide plasma, urine and faecal samples for metabolite profiling and structural identification (Part 2)

7.1.2 Secondary Objectives

- To obtain information regarding the oral PK of total radioactivity, KD025 and its metabolites KD025m1 and KD025m2, in plasma
- To obtain information regarding the IV PK of [¹⁴C]-KD025 in plasma (Part 1)
- To determine the routes and rates of elimination of [¹⁴C]-KD025 and associated total radioactivity (Part 2)
- To evaluate the extent of distribution of total radioactivity into blood cells (Part 2)
- To assess the qualitative and quantitative metabolic profile of [¹⁴C]-KD025 and carry out the structural elucidation of the main metabolites in plasma (accounting for $\geq 10\%$ of circulating total radioactivity) and in urine and faecal samples (accounting for $\geq 10\%$ of administered dose; Part 2)
- To provide additional safety and tolerability information for KD025

7.2 Endpoints

7.2.1 Primary Endpoints

- Absolute bioavailability (F) of KD025

- Mass balance recovery of total radioactivity in all excreta (urine and faeces): Ae, %Ae, Cum Ae and Cum %Ae
- Collection of plasma, urine and faeces for metabolite profiling and structural identification

7.2.2 Secondary Endpoints

- Assessment of oral PK of KD025, KD025m1 and KD025m2 and total radioactivity by calculation of: Tlag, Tmax, Cmax, AUC(0-last), AUC(0-inf), AUC%extrap, lambda-z, T1/2, CL/F (KD025 only), Vz/F (KD025 only) and MRT.
- Assessment of IV PK of [¹⁴C]-KD025 by calculation of: Tmax, Cmax, AUC(0-last), AUC(0-inf), AUC%extrap, lambda-z, T1/2, CL, Vz, Vss and MRT.
- Determination of routes and rates of elimination of ¹⁴C- by metabolite profiling and structural identification in plasma, urine and faeces.
- Evaluation of whole blood:plasma concentration ratios for total radioactivity
- Amount and structure of metabolites in plasma (accounting for $\geq 10\%$ of circulating total radioactivity), urine and faeces (accounting for $\geq 10\%$ of administered dose).
- To provide additional safety and tolerability information for KD025 by assessing: AEs, vital signs, electrocardiograms (ECGs), physical examinations and laboratory safety tests.

8 Study Design

8.1 Study Plan

This is a single centre, non-randomised, open-label, two-part study in healthy male subjects. Six subjects will participate in both parts of the study.

8.1.1 Study Plan Part 1

Part 1 is an open-label, non-randomised single oral dose followed by an IV microtracer assessment in 6 healthy male subjects. On Day 1 subjects will receive a single dose of KD025 (Treatment A), in the fed state. Subjects will then receive an IV dose of [¹⁴C]-KD025 (100 µg, a 'microdose') containing NMT 37 kBq (1000 nCi) [¹⁴C], as a 15 min IV infusion (Treatment B), 1.75 h after the oral dose administration (Treatment A) ie, 15 min before the expected Tmax (2 h) for the oral dose.

Treatment	Investigational Medicinal Product (IMP)
A	KD025 Tablet, 200mg
B	[¹⁴ C]-KD025 solution for infusion, 20 µg/mL (100 µg in 5mL), containing NMT 37 kBq (1000 nCi) [¹⁴ C], as a 15 min IV infusion, 100 µg

¹⁴C: carbon-14, kBq: Kilobecquerel, IV: Intravenous, µCi: Microcurie, nCi: Nanocurie, NMT: Not more than.
All IMPs are described as free base equivalent.
Details of IMPs can be found in Section 5.2

It is planned to enrol 6 subjects so there are 4 evaluable subjects. An evaluable subject for Part 1 is defined as a subject who has sufficient data for evaluation of the primary bioavailability objective of the study.

All subjects will undergo preliminary screening procedures to determine their eligibility for Parts 1 and 2 of the study at the screening visit (Day -28 to Day -2 of Part 1). Subjects will be admitted to the clinical unit on the evening prior to IMP(s) administration (Day -1) for confirmation of eligibility and baseline procedures. Subjects will be dosed on the morning following admission (Day 1). Following an overnight fast (approximately 10 h), subjects will consume a standard breakfast and will receive a single dose of KD025 (Treatment A) 30 min after the start of breakfast. One hour and 45 min post Treatment A administration, subjects will receive an IV infusion of [¹⁴C]-KD025 solution (Treatment B). Subjects will remain resident in the clinic until up to 48 h post-oral dose (up to Day 3). The minimum washout period between dose administrations in Part 1 and 2 will be 7 days.

8.1.2 Study Plan Part 2

Part 2 is an open-label, non-randomised ADME assessment in 6 healthy male subjects. Following a minimum washout period of 7 days, subjects who participated in Part 1 of the study will be admitted to the clinical unit for participation in Part 2 of the study. On Day 1 each subject will receive a single oral administration of 200 mg [¹⁴C]-KD025 capsule containing (NMT 9.8 MBq) (215 µCi) [¹⁴C] (Treatment C) on the morning of Day 1 after a standard breakfast.

Treatment	IMP Dose
C	[¹⁴ C]-KD025 capsule, containing NMT 9.8 MBq (215 µCi) ¹⁴ C, 200 mg

¹⁴C:carbon-14, MBq: megabecquerel, µCi: Microcurie, NMT: not more than. IMP is described as free base equivalent.

Details of IMPs can be found in Section 5.2

A subject in Part 2 will be considered evaluable if they have provided biological samples for up to 168 h after drug administration or have demonstrated >90% mass balance recovery, or have <1% of the administered dose eliminated in excreta for two consecutive days, whichever is the sooner.

[figure not shown]
Approximately 7 days after subjects have been discharged from Part 1 of the study, subjects will be admitted to the clinical unit on the evening of the day prior to IMP administration (Day -1) for the confirmation of eligibility and baseline procedures. Subjects will be dosed on the morning following admission (Day 1). Following an overnight fast (approximately 10 h), subjects will consume a standard breakfast and will receive a single dose of [¹⁴C]-KD025 capsule (Treatment C) 30 min after the start of breakfast. Subjects will remain resident in the clinic until up to 168 h after dosing (up to Day 8). It is planned that subjects will be released as a group when all subjects have achieved a mass balance cumulative recovery of >90% or if <1% of the dose administered has been collected in urine and faeces within 2 separate, consecutive 24 h periods. This may result in the subjects being discharged as a group prior to completion of the planned residency period. Once the discharge criteria or the planned residency period has been achieved, the subjects will undergo discharge assessments and collection of all samples (blood, urine and faeces) will be stopped.

If mass balance criteria have not been met by all subjects on Day 8, the residency period for the subjects not achieving the release criteria may be extended up to a maximum of 216 h post-dose (Day 10). During the additional residency period only urine and/or faeces will be collected. If the criterion is still not met by Day 10, or if additional residency

is not considered appropriate or necessary, then home collections of urine and/or faeces may be requested at the discretion of the investigator for individual subjects. To ensure ongoing wellbeing of the subjects, a follow-up phone call will take place 5 to 7 days post-discharge from the study or after the end of the last collection period.

An overview of the study is presented below (Figure 1):

Figure 1 Study Sequence

^a Discharge time relative to oral dose, 48 h post-dose.

^b Subjects who participated in Part 1 will be admitted to the clinical unit on Day -1 of Part 2 after a minimum washout period of 7 days.

^a If mass balance criteria have not been met by all subjects on Day 8, the residency period for the subjects not achieving the release criteria may be extended up to a maximum of 216 h post-dose (Day 10). During the additional residency period only urine and/or faeces will be collected. If the criterion is still not met by Day 10, or if additional residency is not considered appropriate or necessary, then home collections of urine and/or faeces may be requested at the discretion of the investigator for individual subjects.

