5.3 Previous Study Findings

5.3.1 Non-clinical Data Summary

Nonclinical pharmacology studies demonstrate the potential of KD025 to have a therapeutic benefit in a number of indications, particularly in autoimmune disease through effects on Th17-type immune responses, and idiopathic pulmonary fibrosis (IPF) through anti-fibrotic mechanisms [12].

Solubility of KD025 is pH dependent ie, it is 100 µg/mL at pH 2.7, ~4 µg/mL at pH 6.5 and ~3 µg/mL at pH 7.4. The lower solubility at higher pH could potentially impact absorption of KD025 under physiological conditions.

KD025 plasma exposure generally increased with dose, was dose proportional or greater than dose proportional, and showed some accumulation. The elimination half-life of KD025 was variable in nonclinical studies with calculated values of approximately 2 h in mice, 1 to 7 h in rat and rabbit, and 1 to 3 h in dog.

KD025 undergoes first pass metabolism in all evaluated species after oral administration to form a ROCK2 active metabolite, KD025m1 and a metabolite that is relatively less active against ROCK2, KD025m2.

Distribution studies performed in rats with oral administration of carbon-14 [¹⁴C]-KD025 demonstrated distribution primarily into tissues associated with elimination (gastrointestinal [GI], liver, kidney, urinary bladder), adrenal gland, and exocrine glandular tissue. All tissues demonstrated clearance and no appreciable radioactivity was observed in the brain. Melanin-containing tissues (uveal tract and pigmented skin) demonstrated higher tissue retention, indicating some affinity of KD025 for melanin.

[¹⁴C]-KD025 excretion was similar in male and female rats and was predominantly via the faecal route (~90%), while urine accounted for a smaller proportion of excretion (<1%).

Based on in-vitro assessment, cytochrome P450 (CYP)3A4 and CYP1A2 were the predominant CYP isoforms responsible for the metabolism of KD025, although CYP2C8, CYP2D6 and Uridine 5'-diphospho-glucuronosyltransferase (UGT)1A9 may also contribute to a lesser extent. Metabolism of KD025 to KD025m1 was CYP3A4 and CYP2C8 dependent. Metabolism of KD025 to KD025m2 was CYP3A4 dependent with further metabolism of KD025m2 dependent on UGT1A1 with no to little contribution from CYP enzymes.

KD025 and the active metabolite KD025m1 is > 99% bound to human, dog and rat plasma proteins. KD025m2 is > 99% bound to human plasma protein.

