9.2 Inclusion Criteria

1. Healthy males
2. Age 30 to 65 years of age
3. Good state of health (mentally and physically) as indicated by a comprehensive clinical assessment (detailed medical history and a complete physical examination), ECG and laboratory investigations (haematology, clinical chemistry and urinalysis)
4. Body weight ≥ 50 kg
5. Body mass index (BMI) of 18.0 to 35.0 kg/m²
6. Must be willing and able to communicate and participate in the whole study

7. Must have regular bowel movements (ie, average stool production of ≥ 1 and ≤ 3 stools per day)
8. Subjects must have participated in Part 1 in order to be eligible for Part 2
9. Must provide written informed consent
10. Must agree to adhere to the contraception requirements defined in Section 9.4.

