10.3.3 Discharge from the Clinical Unit

Part 1

A subject will be allowed to leave the premises following completion of study-specific procedures at 48 h post-dose providing that:

- no AEs have been reported during the study visit
- the subject responds in the affirmative when asked if they are feeling well

If any of these conditions are not met, then the subject will only be allowed to leave the clinical unit with the authorisation of the investigator or appropriately qualified delegate.

There will be no continued provision of the study intervention or treatment for subjects as this study involves healthy volunteers only.

Part 2

A subject will be allowed to leave the premises following completion of study-specific procedures at 168 h post-dose providing that:

- no AEs have been reported during the study visit
- the subject responds in the affirmative when asked if they are feeling well

Subjects will be dosed on the morning of Day 1 following a standard breakfast, and will remain resident in the clinical unit until up to 168 h after dosing (up to Day 8). It is planned that subjects will be released as a group when all subjects have achieved a mass balance cumulative recovery of >90% or if <1% of the dose administered has been collected in urine and faeces within 2 separate, consecutive 24 h periods. This may result in the subjects being discharged as a group prior to completion of the planned residency period. Once the discharge criteria or the planned residency period has been achieved, the subjects will undergo discharge assessments and collection of all samples (blood, urine and faeces) will be stopped. If mass balance criteria have not been met by all subjects on Day 8, the residency period for the subjects not achieving the release criteria may be extended up to a maximum of 216 h post-dose (Day 10, 2 additional 24 h periods). If the criterion is still not met by Day 10, or if additional residency is not considered appropriate or necessary, then home collections of urine and/or faeces may be requested at the discretion of the investigator for individual subjects.

If any of these conditions are not met, then the subject will only be allowed to leave the clinical unit with the authorisation of the investigator or appropriately qualified delegate.

There will be no continued provision of the study intervention or treatment for subjects as this study involves healthy volunteers only.

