11.1 Food and Fluid Intake

Subjects will be allowed water up to 1 h before the scheduled dosing time and will be provided with 240 mL of water at 1 h post-dose. Water will be allowed ad libitum after 1 h post-dose. Decaffeinated fluids will be allowed ad libitum from lunch time on the day of dosing. In Part 1, the water restrictions before and after dosing only apply to the oral dose. If, for technical reasons, dosing is delayed for more than 2 h beyond the expected dosing time, subjects will receive 200 mL of Lucozade Sport at the originally scheduled dosing time, or earlier if possible.

Breakfast will be controlled by clinical staff members on Day 1 for both study Parts. The start and stop time of the meal and the percentage consumed must be recorded in the source.

Subjects will be provided with a light snack and will fast from all food and drink (except water) until the following morning, when they will be provided with a standard breakfast.

The breakfast should be consumed over a maximum period of 25 min, with oral dosing occurring 30 min after the start of breakfast. Subjects should be encouraged to eat their meal evenly over the 25 min period. It is acknowledged that some subjects will take less time to eat, but dosing should still occur 30 min after the start of breakfast.

The acceptable deviation for the pre-dose meal from the nominal time point is:

- Pre-dose meal will be provided within \pm 5 min of the nominal time point

Lunch will be provided at approximately 4 h post-dose, an evening meal at approximately 10 h post-dose and an evening snack at approximately 14 h post-dose. On subsequent days, meals will be provided at appropriate times.

Part 2 only: If an individual subject has not experienced a bowel movement in any 36-h period post-dose, fluid intake should be increased and administration of a mild laxative (eg, prune juice or a mild stool softener) should be implemented.

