9.3.1 Definition of Mass Balance Parameters

A list of mass balance parameter definitions with reporting specifications are provided in Table 3.

Table 3 Mass Balance Parameters and Reporting Specifications

Parameter	Definition	Units	DP or SF	No. of DP/SF
Ae(urine)	amount of total radioactivity excreted in urine	Mass unit equiv	SF	3
%Ae(urine)	amount of total radioactivity excreted in urine expressed as a percentage of the radioactive dose administered	%	DP	2
CumAe(urine)	cumulative amount of total radioactivity excreted in urine	Mass unit equiv	SF	3
Cum%Ae(urine)	cumulative amount of total radioactivity excreted in urine expressed as a percentage of the radioactive dose administered	%	DP	2
Ae(faeces)	amount of total radioactivity excreted in faeces	Mass unit equiv	SF	3
%Ae(faeces)	amount of total radioactivity excreted in faeces expressed as a percentage of the radioactive dose administered	%	DP	2
CumAe(faeces)	cumulative amount of total radioactivity excreted in faeces	Mass unit equiv	SF	3
Cum%Ae(faeces)	cumulative amount of total radioactivity excreted in faeces expressed as a percentage of the radioactive dose administered	%	DP	2
Ae(total)	amount of total radioactivity excreted in urine and faeces combined	Mass unit equiv	SF	3
%Ae(total)	amount of total radioactivity excreted in urine and faeces combined expressed as a percentage of the radioactive dose administered	%	DP	2
CumAe(total)	cumulative amount of total radioactivity excreted in urine and faeces combined	Mass unit equiv	SF	3
Cum%Ae(total)	cumulative amount of total radioactivity excreted in urine and faeces combined expressed as a percentage of the radioactive dose administered	%	DP	2

DP=decimal places

SF=significant figures

Home collections of urine and/or faeces may be requested at the discretion of the investigator for individual subjects. All mass balance parameters will be calculated over all available time points, including home collection, if applicable.

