- the cumulative % amount of the total radioactive dose excreted in urine, ie $Cum\%Ae(\text{urine})$, and the cumulative % amount of the total radioactive dose excreted in faeces, ie $Cum\%Ae(\text{faeces})$, will be calculated by the incremental summation of the $\%Ae(<\text{matrix}>)$ across all collection intervals (where matrix is either urine or faeces). The % amount of the total radioactive dose excreted in the pre-dose sample should not be included in the calculation of the cumulative % of dose excreted.
- the cumulative % amount of the total radioactive dose excreted in urine and faeces combined, ie $Cum\%Ae(\text{total})$, will be calculated for each collection interval using the following formula:

$$Cum\%Ae(\text{total}) = Cum\%Ae(\text{urine}) + Cum\%Ae(\text{faeces})$$

For urine and faeces, where a subject has failed to void over a particular collection interval the amount excreted (Ae) will be set to zero.

If part of a void over a particular collection interval is missing due to spillage or accidental discarding, the Ae will still be calculated providing other samples have been collected within the interval. Where no other samples are collected within the interval, the data will be set to missing for the purposes of the calculation of Ae, %Ae, CumAe and Cum%Ae. In both scenarios the data will be flagged to highlight a missing void.

Imputation of non-numerical values reported in the urine and faecal dataset (ie concentrations that are BLQ) will be entered as zero for calculation of parameters.

When converting urine collection weights to urine volume (if required), the following conversion factor will be used:

$$1.02 \text{ g of urine} = 1 \text{ mL of urine}$$

This will be calculated in SAS as follows:

$$\text{Urine weight (g)} / 1.02 = \text{Urine volume (mL)}$$

If total radioactivity concentrations in urine have been provided in mass unit/g units, the following conversion (if required) will be performed using SAS:

$$\text{Concentration (mass units/g)} * 1.02 = \text{Concentration (mass units/mL)}$$

The radioactivity associated with toilet paper may be determined if considered necessary. The results will be reported for each subject as a single value for the whole collection period and included in the calculation of overall cumulative excretion and recovery parameters.

The following dose levels will be used for mass balance analysis and will be applied with the following constraints:

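### Minor: the <1% release limb in Part 2 requires no faecal sample, so two stool-free 24 h periods could take a subject at 90% recovery or less out of the optional Day 8 extension

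*Protocol*

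**What the plan says.** Protocol 8.1.2 releases subjects as a group when all have cumulative recovery above 90%, "or if <1% of the dose administered has been collected in urine and faeces within 2 separate, consecutive 24 h periods". The same rule stands in Protocol 3, 10.3.3 and Appendix 3, and in SAP 5.1.2 and Appendix 2. Once the criteria or the planned 168 h are reached, sample collection stops.

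At Day 8 the decision becomes individual: "the residency period for the subjects not achieving the release criteria may be extended up to a maximum of 216 h post-dose". Home collection may be requested at the investigator's discretion, if the criterion is still unmet at Day 10 or if extra residency is not thought appropriate or necessary.

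Other relevant text:
- Protocol 9.2 selects subjects with an average of 1 to 3 stools per day.
- Protocol 11.1 has a provision that begins "If an individual subject has not experienced a bowel movement in any 36-h period post-dose".
- Protocol 5.3.1 gives excretion data for rats only: about 90% faecal and under 1% urinary.
- SAP 9.3.2 states that "where a subject has failed to void over a particular collection interval the amount excreted (Ae) will be set to zero".
- Protocol 3 and 8.1.2 and SAP 3.2.1 use a similar <1% limb, over two consecutive days, to define an evaluable subject.

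**The concern.** The <1% limb treats low recovery over two days as a sign that excretion is nearly complete. That inference is sound when stool was passed and contained little radioactivity. It is weak when no stool was passed, because the amount is then low whatever remains in the gut. The rule does not separate the two cases.

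The consequence arises mainly at Day 8. A subject at 90% or less who meets the limb through two stool-free periods has formally achieved the release criteria, so the text no longer prompts an extension for him. Excreta not collected cannot be recovered afterwards. Cumulative recovery is a primary endpoint (Protocol 7.2.1), there are at most six subjects, and none is replaced (Protocol 8.4).

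**Working it through.** The plan gives no probability or size for this rule, so there is no figure to reproduce. The check has four parts.

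**1. Does the limb admit the case?** None of the six statements of the rule requires a faecal sample, a minimum recovery or an earliest time. Two stool-free periods with <1% of dose in urine in each satisfy it. If human urinary excretion were as low as in the rat, any two stool-free periods would do so.

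**2. How long a gap is needed?** 2 × 24 h = 48 h at least. The Protocol 11.1 provision applies at 36 h, which is 48 − 36 = 12 h earlier. The gap must also line up with the collection clock: a randomly placed gap of g hours (48 to 72) contains two whole periods with chance (g − 48)/24.

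**3. How likely is it?** The documents cannot say. An illustrative simulation (3,000 runs per scenario) used these assumptions, none of which is in the plan:
- gamma-distributed stool intervals, mean 16 or 24 h, shape 1 or 4;
- mean transit of 36 or 72 h;
- total urinary recovery of 1% or 5%, and 97% of dose excretable;
- mean response lag of 8 h after the 36 h provision applies.

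It counted any two consecutive stool-free periods up to 168 h that met the limb, together with recovery of 90% or less at 168 h.

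| 36 h provision | Per subject | At least one of six |
|---|---|---|
| Effective | about 0 to 0.9% | about 0 to 5.5% |
| No effect at all | about 0 to 15% | about 0 to 63% |

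The high end of the second row needs random stools averaging one a day and slow transit.

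**4. How large is the effect?** If d points of dose go uncollected in one of n subjects, the mean falls by d/n. The plan enrols six and regards four evaluable subjects as sufficient.

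| d (assumed) | n = 6 | n = 4 |
|---|---|---|
| 1 | 1/6 = 0.17 | 1/4 = 0.25 |
| 10 | 10/6 = 1.67 | 10/4 = 2.5 |
| 20 | 20/6 = 3.33 | 20/4 = 5.0 |

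If the other subjects are equal, the median does not move and the minimum falls by d. If nothing remains to be passed, d = 0.

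**The case against.** The strongest reply is that very little is lost. At Day 8 the subject has completed the whole planned 168 h, which alone makes him evaluable. The extension is only optional. Stool habit at entry and the 36 h provision make a gap of 48 h or more unlikely. Home collection is available at discretion, and "All mass balance parameters will be calculated over all available time points, including home collection, if applicable". If an AE has been reported, "then the subject will only be allowed to leave the clinical unit with the authorisation of the investigator or appropriately qualified delegate". The listings in SAP 9.4.3 show each subject's values, so an empty final period is visible. All this stands and is why the point is minor. None of these safeguards is tied to the <1% limb, however: the bowel criterion is an average, the 36 h provision cannot guarantee a stool, and the AE condition has nothing to do with recovery.

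Three stronger readings are tempting, and the documents do not support them:
- **That scoring a non-void as zero biases recovery.** Zero is the correct amount for an interval in which nothing was passed. The gap is in the release rule.
- **That recovery in this trial will be materially understated.** No human route, rate or retained amount is given, and the rat data cannot settle it.
- **That a trial conclusion is at risk.** SAP 9.4.4 plans descriptive statistics only, and no decision rule uses the mean.

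A reader might also infer early discharge of the group. Before Day 8, group release requires all subjects to qualify, so one subject's stool-free periods cannot release the group alone.

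**Conclusion.** The gap is real on the text, and it is minor. The limb can be met without any faecal sample. A subject at 90% recovery or less could then lose the prompt for an optional extension, and his cumulative recovery could be understated. That requires two whole collection periods without stool, urine under 1% in each, recovery still at 90% or less, and radioactivity still to be passed. The effect on the mean is d/n with d unknown; only the accuracy of a reported primary endpoint is exposed.

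If it happened, the value would probably stay in the whole-study summary. A true non-void is not among the SAP 6.3 examples for exclusion, although a subset dataset could remove him. If other subjects were extended to Day 10, SAP 9.4.1 would give one table that carries his last value forward and one that does not.

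This reads <1% as applying to each period. The wording leaves open whether it means each period or the two together, and whether the pair must be the latest one.

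**What to change.** Keep the existing sentence in Protocol 3, 8.1.2, 10.3.3 and Appendix 3, and in SAP 5.1.2 and Appendix 2. Directly after its reference to the two 24 h periods, add: *, provided that at least one faecal sample was collected in those two periods*. Add the same proviso to the <1% wording in the evaluability definition (Protocol 3 and 8.1.2, SAP 3.2.1), so that the two criteria agree. In the SAP 9.4.3 listings, flag any subject whose collection ended with a stool-free period.

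The clause can be checked by counting. Classify each of the seven 24 h periods to 168 h as stool or no stool, and as under 1% or not: 4^7 = 16,384 logical patterns (not probabilities). Read as the latest two periods, the current limb is met in 4^5 × 2 × 2 = 4,096. Both periods are stool-free in 4^5 = 1,024 of these. The proviso refuses exactly those and no others, leaving 4,096 − 1,024 = 3,072. Requiring a stool in each period would also refuse 4^5 × 2 = 2,048 patterns in which one of the two has a stool, which is more than the problem needs.

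One limit remains: the clause sets no earliest time and no minimum recovery, so a pair with one low-activity stool still qualifies.

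The cost is one clause in six places, the same proviso in three more, and one listing flag. A subject with two stool-free periods, or before Day 8 the group, may stay longer within the existing 168 h and 216 h limits or collect at home. Extension stays discretionary. The clause governs only when excreta collection ends and proposes no treatment or laxative rule.
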